### 11.1.4 Reporting of AEs and SAEs

All AEs must be recorded in the case report form, defining relationship to IMP and severity. The frequency of each AE should always be recorded to indicate if the event is intermittent, continuous, one-time event etc. If the same AE occurs repeatedly at approximately the same strength in the same patient, this AE should be counted only once. If any aspect of the AE changes (including but not limited to severity, frequency, causality), a new AE should be recorded. AE start and end dates should be clearly defined in the CRF.

**As soon as the Investigator is aware of a potential SAE, he/she should report the SAE to the Pharmacovigilance (PV) CRO by fax or e-mail, and in any case no later than 24 hours after the knowledge of such a case. In case of questions regarding an SAE, the investigator or authorized study personnel can contact the PV CRO monitor by phone. The contact information, is provided in the Investigator Site File.**

At the time of the call, the Investigator must provide as a minimum requirement, the Patient number, birth date, nature of the SAE, and a preliminary assessment of causality. The Investigator should follow-up the initial notification of the potential SAE by faxing/e-mailing a copy of the form to PV CRO at the number/address provided in the Investigator Site File. The SAE reporting form should be received to the PV CRO within 24 hours after knowledge of such a case.

Follow-up information on an existing SAE that is fatal or life-threatening should be reported by the Investigator to PV CRO within 5 days after the initial report. Where appropriate, hospitalisation or autopsy reports should be made available. All SAEs will be followed up until resolution (i.e., asymptomatic, stabilisation or death).

AE's should be reported for the entire study duration up to and including the follow up period. Following completion of the study, if the Investigator becomes aware of any AE that is potentially related to the IMP, the Sponsor should be notified.

## 11.2 Serious Adverse Reactions and Unexpected Adverse Reactions

### 11.2.1 Definitions

#### **Adverse Reaction:**

All noxious and unintended responses to a medicinal product related to any dose should be considered adverse drug reactions.

The phrase "responses to a medicinal product" means that a causal relationship between a medicinal product and an adverse event is at least a reasonable possibility i.e. the relationship cannot be ruled out.

For marketed medicinal products, an adverse reaction is a response to a drug which is noxious and unintended and which occurs at doses normally used in man for prophylaxis, diagnosis, or therapy of disease or for modification of physiological function.

***Unexpected Adverse Reaction:***

An adverse reaction, the nature or severity of which is not consistent with the applicable product information (e.g. Investigator's Brochure for an unauthorised investigational product or similar product information sheet such as the Summary of Products Characteristics (SPC)).

***Suspected Unexpected Serious Adverse Reaction (SUSAR):***

Any serious adverse reaction that might be related to the IMP and are unexpected according to the definition above.

### **11.2.2 Reporting of suspected unexpected serious adverse reactions**

Suspected unexpected serious adverse reactions (SUSARs) will be reported by PV CRO according to appropriate Competent Authority and Ethics Committee requirements. SUSARs will be reported to Investigators according to ICH Good Clinical Practice and to local regulations. SUSAR reporting to the Competent Authorities and Ethics Committees will be performed according to local regulations in an unblinded manner. The Competent Authorities will be notified of all SUSARs through the Eudravigilance database.

Fatal and life-threatening SUSARs should be reported by PV CRO as soon as possible to the Competent Authorities and Ethics Committees according to local regulations, and in any case no later than seven calendar days, after knowledge by PV CRO of such a case. Relevant follow-up information on the case will be subsequently communicated within an additional eight days. All other SUSARs shall be reported to the Competent Authorities concerned and to the Ethics Committee concerned according to local regulations as soon as possible but within a maximum of fifteen days of first knowledge by PV CRO.

### **11.3 Differentiation of Treatment Failure and AE**

Please note, that the lack of improvement of the symptoms of AD is not an AE and should be reported as treatment failure.

### **11.4 Pregnancy Reporting**

If a patient or a patient's partner becomes pregnant during the study, the patient should inform the study site as soon as possible. Upon confirmation of the pregnancy, the patient must be withdrawn from study drug but may continue study participation. The Investigator must complete a study-specific Pregnancy Form upon confirmation of a pregnancy and send it to the Sponsor within 24 hours of confirmation of the pregnancy.

Post-treatment follow-up should be done to ensure patient safety. Pregnancy is not itself an AE or SAE, however maternal/foetal complications or abnormalities will be recorded as AEs or SAEs as appropriate. The investigator will follow the pregnancy until completion (or until pregnancy termination) and notify the Sponsor of the outcome as a follow up to the initial Pregnancy Form.

## 12 STATISTICAL METHODOLOGY AND DATA MANAGEMENT

### 12.1 Study Design

This clinical trial employs a randomized, double-blind, placebo-controlled parallel group design. Randomisation is used to minimise assignment bias and to increase the likelihood that known and unknown patient attributes (e.g. demographic characteristics) are evenly balanced across the treatment groups. Blinding is used to reduce potential bias during data collection and evaluation of safety and efficacy. The use of placebo as comparator is justified as a reasonable design to assess safety and efficacy in patients based on the brevity of the study duration and the absence of any possible long-term irreversible damage that may be the result of placebo treatment. A full description of the study design is presented in Section 6 above.

### 12.2 Randomisation

Approximately 220 patients will be randomized into double-blind treatment groups in a 1:1 ratio by an IWRS.

- 2g DS107 (4 DS107 capsules) administered once-daily for 16 weeks
- Placebo (4 placebo capsules) orally administered once-daily for 16 weeks

A randomization list permuted by blocks and stratified by site will be generated by the Sponsor or its designee. The randomization schedule with study drug assignments will be generated prior to the start of the study and will be known only to the individuals responsible for labelling the study drug, the statisticians generating the schedule and the IWRS team responsible for implementing the schedule. The IWRS will assign a medication kit number to each patient and the contents will be based on the randomization code.

At the investigational site, each patient will be assigned a patient identifier number during screening that will be used on all patient documentation. The patient identifier number will contain the site number and the patient number assigned in numerical order at the Screening Visit (e.g.: 102-10 for the tenth patient screened at the site number 02). Patient numbers will be assigned in ascending order starting with 01.

The treatment assignment procedure will use blocks of sufficient size to maintain a blind and balance across treatment arms. Following successful completion of the screening/baseline evaluations and confirmation that the patient is eligible for participation, the patient will be randomised to treatment. This will be performed by the Investigator using the IWRS which will assign a medication number to the patient.

### 12.3 Estimation of Sample Size

In the Phase 2a trial, IGA response rates of 21.6% and 11.8% were observed for DS107 and placebo respectively resulting in a difference in response rates of 9.8%. Due to the prolonged treatment period of 16 weeks, a clinically relevant difference in IGA response rates of 15% was expected for the current study.

Assuming a placebo response rate of 12% and a true response rate difference of 15% at Week 16 and using a two-sided Chi-Square test on a significance of 5%, then 220 evaluable patients (110 patients per treatment arm) will be needed for 80% power to detect this difference as statistically significant. As the following table shows, the number of patients needed for the

discovery of a 15% response rate difference depends also on the placebo response rate shown in the left column of the table as decimal numbers:

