## 6 STUDY DESIGN

This is a randomised, placebo-controlled, double-blind, parallel group, multi-centre 2-arm Phase 2 study to investigate the efficacy of orally administered DS107 in AD patients.

It is planned that at least 220 patients suffering from moderate to severe AD will be included in this study. All patients will sign an informed consent and undergo screening for study eligibility.

Before the comparative treatment period can commence, patients will return to the site for a baseline assessment of their disease and eligible patients will be randomly allocated to one of the treatment regimens in a 1:1 randomization:

[figure not shown]
- 2g DS107 (4 DS107 capsules) orally administered once daily for 16 weeks
- Placebo (4 placebo capsules) orally administered once daily for 16 weeks

There is a 4 week follow-up period.

To maintain the double-blind conditions, DS107 capsules and placebo will be identical in appearance.

A schematic diagram of the overall timeframe of the study is given in Figure 2.

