## 7.5 Withdrawal of Patients

Patients have the right to withdraw from the study at any time for any reason without penalty. The Investigator must explain this to the patient and that this will in no way prejudice their future treatment. The Investigator also has the right to withdraw patients from the study if he feels it is in the best interest of the patient or if the patient is uncooperative or non-compliant. It is understood by all concerned that an excessive rate of withdrawal can render the study uninterpretable, therefore, unnecessary withdrawal of patients should be avoided. Should a patient decide to withdraw, all efforts will be made to complete and report the observations, particularly the follow-up examination, as thoroughly as possible.

The Investigator or one of his or her staff members should contact the patient either by telephone or through a personal visit to determine as completely as possible the reason for the withdrawal, and record the reason in patient's source document and case report form (CRF). A complete final early termination evaluation at the time of the patient's withdrawal should be made with an explanation of why the patient is withdrawing from the study when ever possible. If the reason for removal of a patient is an adverse event or an abnormal laboratory test result, the principal specific event or test will be recorded. Patients who discontinue the study before Week 16/Visit 7 visit will be asked to come for an early termination visit as soon as possible and have the assessments listed at Week 16/Visit 7 performed. They will also be asked to return two weeks later for the safety assessments listed at Week 18/Visit 8.

Patients who develop Grade 3 or higher National Cancer Institute Common Terminology Criteria for Adverse Events (NCI-CTCAE), that is determined to be possibly or probably attributable to the study drug will be discontinued.

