## **7.6 Patient Replacement**

Patients who are withdrawn from the study due to an adverse event or lack of effect will not be replaced. Patients who are withdrawn for other reasons (such as lost to follow up, personal reasons) may be replaced.

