### 1.1 Study Objectives

The primary objective of this clinical trial is to compare the efficacy of orally administered DS107 (2g) versus placebo, in the treatment of adult patients with moderate to severe AD. The secondary objective is to assess the safety of orally administered DS107 (2g) versus placebo, in adult patients with moderate to severe AD.

It is planned to test the trial medication versus placebo in a total of 220 patients.

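### 220 is used both as the evaluable number needed for 80% power and as the number randomised; the slack is about three patients, with no allowance for missing Week 16 data

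*Protocol*

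**What the plan says.** Protocol 12.3, repeated in SAP 2, sets out the calculation for the vIGA-AD response: "Assuming a placebo response rate of 12% and a true response rate difference of 15% at Week 16", tested by a two-sided chi-square test at 5%. It concludes "then 220 evaluable patients (110 patients per treatment arm) will be needed for 80% power". The accompanying table gives 108.4 per arm for a 12% placebo rate at 80% power. The same estimates are assumed to hold for EASI-75.

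The number to be randomised is the same. The Protocol synopsis gives 220 as the total randomised. Protocol 12.2 says "Approximately 220 patients will be randomized into double-blind treatment groups in a 1:1 ratio by an IWRS", as do Protocol 10.5 and SAP 1.5 in near-identical words. SAP 1.1 says "It is planned to test the trial medication versus placebo in a total of 220 patients". Protocol 6 is slightly more open: "It is planned that at least 220 patients suffering from moderate to severe AD will be included in this study".

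Neither sample-size section gives a dropout rate or an inflation step, although Protocol 7.5 warns that "an excessive rate of withdrawal can render the study uninterpretable". On replacement, Protocol 7.6 says "Patients who are withdrawn from the study due to an adverse event or lack of effect will not be replaced"; withdrawals for other reasons may be replaced, at discretion. No section defines 'evaluable'.

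**The concern.** A chi-square calculation for a Week 16 response counts patients with a Week 16 outcome. Using that number as the recruitment target assumes that almost nobody lacks one. This is a 16-week trial run during COVID-19, and its own protocol treats withdrawal as a threat.

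The 80% matters because it is the figure a reader would use to judge how informative a negative result is. If some Week 16 values are missing, the design has less power than stated, and neither document lets the reader see how much less.

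**Working it through.** **Inputs.** From Protocol 12.3 and SAP 2: p1 = 0.12, p2 = 0.12 + 0.15 = 0.27, difference 0.15, two-sided alpha 0.05, 1:1 allocation. The mean rate is 0.195. The loss rates below are assumed and taken as equal in both arms, because the documents give none.

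**Step 1: reproduce the plan's figure.** With pooled variance under the null and no continuity correction,

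n per arm = [1.960 × √(2 × 0.195 × 0.805) + 0.842 × √(0.12 × 0.88 + 0.27 × 0.73)]² / 0.15²

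= [1.960 × 0.5603 + 0.842 × 0.5502]² / 0.0225 = 108.3.

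The plan's table shows 108.4, and every other cell of that table reproduces to within 0.1. Rounding up to 110 per arm is sound. Nothing has been miscalculated.

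**Step 2: power at a given number per arm.**

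Power = Φ[(0.15 × √n − 1.960 × 0.5603) / 0.5502].

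At n = 110 this is Φ(0.863) = 80.6%.

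**Step 3: the slack.** A total of 217 evaluable (108.5 per arm) gives Φ(0.844) = 80.1%. A total of 216 (108 per arm) gives Φ(0.837) = 79.9%. So three patients of 220, about 1.4%, can be lost before power falls below 80%.

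**Step 4: larger losses from 220 randomised, with no replacement and no information recovered.**

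| Assumed share without a Week 16 value | Evaluable per arm | Power, one endpoint |
|---|---|---|
| 0% | 110 | 80.6% |
| 5% | 104.5 | 78.6% |
| 10% | 99 | 76.3% |
| 15% | 93.5 | 73.9% |
| 20% | 88 | 71.3% |

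**Step 5: partial recovery.** The primary analysis is a GLMM over visits on the FAS, so a patient's earlier visits carry some information about Week 16. The documents do not say how much. If half were recovered (an assumption), 10% missing acts like a 5% loss and gives about 78.6%; 20% missing acts like a 10% loss and gives about 76.3%.

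**Step 6: COVID-19 phone visits.** Protocol Appendix 11 provides them for Weeks 4, 8, 12, 18 and 20. There is none for Week 16, and neither vIGA-AD nor EASI is on the list of phone assessments. A visit replaced by a phone call therefore yields no primary-endpoint data, and one at Weeks 4 to 12 also removes data from which the GLMM would borrow.

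**The case against.** Several parts of the plan soften the problem, and each deserves credit.

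- *220 is not a cap.* Protocol 6 and SAP 1.2 say at least 220. Protocol 12.9 and SAP 1.6 allow an interim recommendation to change the sample size. Neither sets a target above 220. Those two sections make the interim optional (Protocol 13.12 says it will be done), and its details are left to a separate interim plan.
- *Replacement.* Protocol 7.6 covers loss to follow-up and personal reasons, but it is permissive and rules out two central causes of withdrawal.
- *Withdrawal is not the same as no outcome.* Early leavers are asked to attend an early-termination visit with the Week 16 assessments (Protocol 7.5 and 8.1), and rescue users are set to non-responder (Protocol 12.8.2, SAP 6.1), so they are not missing. However, neither document says that an early-termination value counts as Week 16.
- *The FAS keeps every dosed patient.* If 'evaluable' meant membership of the FAS, nearly all 220 would qualify. But staying in the set does not supply a Week 16 response, and that is what the chi-square calculation counts.

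A reader might go further in three ways that the documents do not support. The first is that any missing Week 16 value breaks the 80%; the rounding to 110 per arm leaves room for about three. The second is that the figures in Step 4 are the power of the planned analysis. They are complete-case chi-square values on an assumed range, while the plan uses a GLMM, so they are best read as the no-recovery end of a range. The third is that the trial's chance of declaring success is below 80%. The stated 80% is for one endpoint, and success on either of two suffices. If EASI-75 behaves alike and the two tests correlate at 0.7 to 0.9 (an assumption), the chance of at least one success at 10% complete loss is about 86% to 82%. That either/or rule raises its own question, which is separate from this one.

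**Conclusion.** The point holds in limited form. The plan requires 220 evaluable patients for 80% power on the vIGA-AD endpoint, randomises about 220, and makes no stated allowance for missing Week 16 data. Losing more than about three unreplaced patients takes single-endpoint power below 80%. With 10% missing it is roughly 76 to 79%, and with 20% missing roughly 71 to 76%. The lower end assumes that no information is recovered and the upper end that half is.

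These figures rest on the plan's own response rates, equal loss in the two arms, an assumed range of loss, and a chi-square approximation to the GLMM. The mitigating provisions narrow the shortfall but do not commit the trial to closing it. This is a missing planning assumption, not a calculation error. It does not invalidate the design, but it should be corrected because the stated power will be used to interpret the result.

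**What to change.** In Protocol 12.3 and SAP 2:

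1. Define 'evaluable' for the power calculation, and say whether an early-termination assessment counts as a Week 16 value.
2. State the assumed proportion without a Week 16 value.
3. Restate single-endpoint power for 220 randomised as a range. For example: about 76 to 79% with 10% missing and 71 to 76% with 20% missing, depending on how much information earlier visits recover; chi-square approximation to the GLMM.
4. Stop using 220 as both the evaluable and the randomised number.

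The cost is a few sentences in each document and a less favourable stated power. No extra patients and no change to the analysis are required. If the sponsor would rather keep 80% than restate it, the alternative is to randomise 110/(1 − d) per arm, where d is the assumed missing proportion. At 10% this is 110/0.9 = 122.2, rounded up to 123 per arm or 246 in total.

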**Number of patients per study group required under the assumptions as follows**  
**Chi-square test, 2 x 2 table, Two Proportions, two-sided.**  
**Sample Size 1 as a function of H1: Proportion 1 and Power.**  
**H1: Proportion 2 - Proportion 1=0,15 Significance Level=0,05 Sample Size 2 / Sample Size 1=1**

H1: Proportion 1 = Response Rate Placebo	Power		
	0,7	0,8	0,9
0,06	63,4	80,3	107,0
0,08	71,2	90,2	120,3
0,10	78,6	99,6	132,8
0,12	85,5	108,4	144,6
0,14	92,0	116,6	155,6
0,16	98,0	124,3	165,9
0,18	103,6	131,4	175,4
0,20	108,8	138,0	184,2

It was assumed that similar estimations apply to the primary endpoint EASI-75.

## 12.4 Blinding and Code Breaking Instructions

All study site personnel, as well as the personnel involved in the monitoring or conduct of the study, will be blinded to the individual patient treatment assignments. Randomisation details will be kept strictly confidential, accessible only in an emergency to authorized persons, until the time of formal unblinding. The blinded code for the trial will be broken only after all patient data has been recorded and verified and the database locked.

Emergency unblinding will be carried out through the IWRS system with relevant site personnel and pharmacovigilance monitors provided with the required system access to carry out unblinding.

## 12.5 Data Analysis

Data analysis will be performed at a contract research organisation (CRO). All computations will be conducted using SAS® Version 9.2 or later. Graphical summaries will be produced using SAS®. A detailed description of the analyses to be performed will be provided in the statistical analysis plan (SAP).

Continuous variables will be summarized in tables and will include the number of patients, mean, standard deviation, median, minimum, and maximum. Categorical variables will be presented in tables as frequencies and percentages.

## 12.6 Analysis Sets

### *Enrolled Set*

The Enrolled Set consists of all patients who sign informed consent.

### *Screen Failures*

Screen Failures are patients from the Enrolled Set who do not meet the eligibility requirements and are withdrawn from the study prior to randomisation.

**Randomised Set**

The Randomised Set consists of all patients who are randomised to the study.

**Safety Analysis Set (SAS)**

The Safety Analysis Set (SAS) consists of all patients who received at least one dose of the medication. SAS is the analysis population for all safety endpoints. Analysis will be done according to the actual treatment patients received.

**Full Analysis Set (FAS)**

The Full Analysis Set (FAS) consists of all patients who were randomised to the study and received at least one dose of study medication. FAS is the primary analysis population for efficacy endpoints. Analysis will be done according to the treatment patients were randomised to.

**Per Protocol Set (PPS)**

The Per Protocol Set (PPS) is the subset of FAS who completed the study without any major violations. Protocol violations will be assessed for each patient in a blinded fashion prior to database lock at a Blind Data Review Meeting (BDRM), and the PPS will also be finalised during this meeting. PPS is a supportive analysis population for efficacy endpoints. Analysis will be done according to the treatment patients were randomised to.

## 12.7 Safety Analysis

Demographic, medical history and physical examination data will be listed for each patient and summarised descriptively.

All AEs recorded during the study will be coded to system organ class and preferred terms using the current version of the Medical Dictionary for Regulatory Activities (MedDRA). AEs will be tabulated and summarised by treatment, relationship to treatment, seriousness and severity.

Clinical laboratory values (haematology and biochemistry) will be listed for each patient by treatment and day. Values outside the laboratory normal ranges will be listed separately with associated comments as to their clinical significance, with potentially clinically significant abnormalities highlighted and summarised by treatment. Most recent clinical laboratory values obtained prior to dosing will be defined as baseline values.

Individual values of vital signs will be listed and summarised descriptively for each treatment and visit.

Concomitant medications (if any), categorised by medication group and subgroup according to the latest version of the World Health Organisation drug dictionary, will be listed and summarised by treatment.

